## **MATERIALS AND METHODS:**

The present parallel randomized controlled trial was conducted to compare the outcomes of wound closure using polypropylene versus subcuticular polyglactin 910 sutures in patients undergoing total knee arthroplasty (TKA).

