### **Patient selection:**

All patients aged 50-80 years, belonging to either sex, diagnosed with end-stage osteoarthritis or post-traumatic arthritis, and scheduled for bilateral primary total knee arthroplasty at the Department of Orthopedics, Indus Hospital and Health Network, Karachi were enrolled in the study. Exclusion criteria included patients having existing skin, neuromuscular, or connective tissue disorders, rheumatoid arthritis, immunosuppression, morbid obesity, and pregnancy. All patients provided voluntary informed written consent before enrolment in the study.

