### **Intervention:**

In all patients undergoing primary TKA, one knee was closed using polypropylene, whereas the other was closed with Polyglactin 910 sutures. All surgeries were performed by the same surgical team using a standard medial parapatellar approach. The number of sutures and wound closure techniques were standardized across both groups.

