### **Outcomes:**

Wound healing was then assessed in the postoperative period at regular intervals (days +3, +7, +15, and +30). Wound-related complications such as surgical site infection (SSI), dehiscence, delayed healing, and Hollander score were recorded. Patient-related outcomes such as pain levels and satisfaction with wound healing were also assessed.

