### **Randomization:**

The patients were randomized assigned into two groups. The samples were allocated into two groups by a simple randomization technique using computer generated random numbers. The

choice of procedure was determined based on whether the number fell into either group A or B. Group A had wound closure via polypropylene suture while Group B with polyglactin 910.

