### **Statistical analysis:**

Data analysis was performed using SPSS version 24.0. After assessing the normality of the data, all continuous variables were represented as medians (IQR). Discrete variables are shown as frequencies and percentages. The Hollander score prediction model was used to evaluate the correlation between the Hollander score and all independent variables. Statistical significance was set at  $P < 0.05$ .

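### Each patient had one knee closed with each suture, but the text calls the trial parallel, does not say how the knee was allocated, and specifies no within-patient comparison

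*Combined protocol and SAP*

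**What the plan says.** All references are to the combined protocol and SAP.

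- **Design label** (Materials and Methods): "The present parallel randomized controlled trial was conducted to compare the outcomes of wound closure using polypropylene versus subcuticular polyglactin 910 sutures".
- **Population** (Patient selection): patients were "scheduled for bilateral primary total knee arthroplasty".
- **Treatment** (Intervention): "In all patients undergoing primary TKA, one knee was closed using polypropylene, whereas the other was closed with Polyglactin 910 sutures".
- **Allocation** (Randomization): "The patients were randomized assigned into two groups", followed by "The samples were allocated into two groups by a simple randomization technique using computer generated random numbers". The groups are defined by suture: "Group A had wound closure via polypropylene suture while Group B with polyglactin 910". Left and right knee are not mentioned.
- **Analysis** (Statistical analysis): medians with IQR, frequencies with percentages, a 0.05 significance level, and one model: "The Hollander score prediction model was used to evaluate the correlation between the Hollander score and all independent variables". No suture comparison is named, and nothing is said about two knees from one patient.
- **Results:** 40 patients enrolled; poor cosmesis in 8 (20%) in each suture group; counts by suture for wound signs; systemic symptoms 7 versus 4 (polyglactin 910 first); a median Hollander score of 6 in both groups, with no visit given. The model coefficients in the text are for age, weight, height and diabetes.

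**The concern.** The trial exists to compare two sutures, and three parts of the text that should support that comparison do not fit together.

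The design label and the patient-level wording of the allocation describe one trial, while the Patient selection and Intervention sections describe another. If patients had been assigned to Group A or B, both knees of a patient would share a suture, contrary to the Intervention section. The text does not say how the knee for each suture was chosen, and any causal reading of the suture comparison rests on that.

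The analysis section then gives no estimate, interval or test for the suture difference, so following it as written leaves the stated aim unanswered. Ignoring the pairing would also act in two directions: it wastes precision on the suture contrast, and it can overstate the evidence for patient-level terms in the Hollander model.

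**Working it through.** The text contains no sample-size or power figure to reproduce. The checks below use counts from the Results.

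**1. Which design do the counts follow?** 8 / 0.20 = 40 per suture group. The comorbidity figures give the number of patients: 33 / 0.825 = 40 and 15 / 0.375 = 40. So 40 patients supply 40 knees to each suture, 80 in all. Two parallel groups of patients would total 40.

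**2. Which allocation fits?** Assigning patients to A or B gives both knees the same suture. Simple randomization of each knee separately would give about half the patients the same suture twice. The Intervention section excludes both. One random number per patient choosing the knee would fit, but the Randomization section does not say so.

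**3. Suture contrast: direction of the error.** For a continuous outcome, the variance of the within-patient difference relative to the unpaired variance is 1 − ρ, so positive ρ makes the unpaired standard error too large. For a binary outcome with 40 pairs and an assumed 50% risk in both knees, the exact type I error of the uncorrected unpaired chi-square at 5% is:

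| Assumed ρ | Type I error |
|---|---|
| 0 | 0.057 |
| 0.3 | 0.023 |
| 0.5 | 0.007 |

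**4. Hollander model: the opposite direction.** Suppose the model used 80 knees as independent rows (not stated). A term that is the same for both knees then has its variance understated by a factor of 1 + ρ. Type I error = 2 × [1 − Φ(1.96 / √(1 + ρ))].
- ρ = 0.3: 1.96 / 1.140 = 1.719, giving 0.086.
- ρ = 0.5: 1.96 / 1.225 = 1.600, giving 0.110.

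**5. Illustration: wound discharge, 24 versus 16 of 40.**
- Unpaired: chi-square = 80 × (24×24 − 16×16)² / 40⁴ = 3.2, P = 0.074. Newcombe 95% CI for the 20-point difference: −1.8 to 39.3.
- Paired: let *a* be the number of patients affected in both knees, which the text does not give. The discordant counts are 24 − *a* and 16 − *a*, and φ = (40*a* − 24×16) / 384. Non-negative φ needs *a* ≥ 9.6, so *a* runs from 10 to 16.

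| *a* | Discordant | φ | Exact McNemar P | Paired score 95% CI (points) |
|---|---|---|---|---|
| 10 | 14 v 6 | 0.04 | 0.115 | −2.0 to 40.1 |
| 12 | 12 v 4 | 0.25 | 0.077 | 0.4 to 38.4 |
| 14 | 10 v 2 | 0.46 | 0.039 | 3.5 to 36.6 |
| 16 | 8 v 0 | 0.67 | 0.0078 | 9.5 to 34.8 |

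The paired interval is slightly wider than the unpaired one near zero correlation. At the extreme pairing (*a* = 16) it is 25.3 / 41.1 = 0.62 of the unpaired width.

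**6. Is discharge typical?** No. The Results text gives 13 knee-level contrasts: erythema at four visits, eight other wound signs, and cosmesis. For a difference of *d* patients, the smallest possible exact P comes at maximum overlap and equals 2^(1−*d*), capped at 1. Discharge (*d* = 8) gives 0.0078. Next are erythema on day 3 (*d* = 5), 0.0625, and cellulitis (*d* = 4), 0.125. The other ten cannot go below 0.25. Discharge is the only contrast that could fall below 0.05.

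**7. Systemic symptoms.** Every patient had both sutures. With full overlap, 7 versus 4 means 7 affected patients; with none, 7 + 4 = 11.

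**The case against.** The best defence is that the design is clear from the Patient selection and Intervention sections, the denominators agree with it, and the design label is one loose word. Read alongside the Intervention section, the allocation text is compatible with one random number per patient. Tables 1 and 2 are not in the text reviewed, and Table 2 may hold tests. Suture may also be among the independent variables of the Hollander model.

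Much of this stands. It limits the point to what the methods text specifies. It does not remove the point: the patient-level wording under Randomization repeats the conflict, the knee is still not mentioned there, and tests in a table would not supply the missing method.

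Three stronger readings are tempting and not supported:

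- **That an unpaired test was run and produced false findings.** No such test appears, no significant suture difference is claimed, and for the suture contrast the error would be conservative.
- **That the knee was not randomized.** The text describes computer-generated randomization. It does not say what the number decided.
- **That a paired analysis would make discharge significant.** This needs at least 14 of the 16 possible patients affected in both knees on the exact test. The pairing is unknown, the possible pairings are not equally likely, and discharge is the best case of 13.

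**Conclusion.** The point holds for the methods text. The trial is a within-patient comparison of 40 knees against 40 knees, which contradicts the parallel label and the patient-level assignment. How the knee was allocated is not stated, and no suture comparison is specified. No reported figure is shown to be wrong.

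The effect of ignoring the pairing depends on the analysis. For the suture contrast the loss is precision: nothing near zero correlation, more as correlation rises. For patient-level terms in the Hollander model, type I error would be about 0.086 or 0.110 instead of 0.05. Those two figures rest on assumed correlations of 0.3 and 0.5 and on the model having used 80 independent rows, neither of which the text states. The gain from correcting the plan is a valid estimate and interval for the trial's own question, and no particular P value should be expected.

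**What to change.** 1. Describe the design as within-patient. Reconcile Materials and Methods, Intervention and Randomization, and state how the knee for each suture was allocated. If it was not randomized, say so, because a paired analysis does not cure that.
2. In Statistical analysis, specify a within-patient suture comparison. For knee-level binary outcomes: the paired 2×2 table, a paired risk difference with 95% CI as the main result, and a McNemar test. For the Hollander score at a stated visit: a within-patient difference with CI, by Wilcoxon signed-rank or, equally acceptable, a mixed model. The same applies to pain and satisfaction if they were recorded per knee.
3. Fit the Hollander model with suture as a term and a patient random effect or patient-clustered standard errors.
4. Report systemic symptoms per patient, outside the suture contrast, unless a rule for attributing them to a knee is stated.
5. Label these analyses post hoc. If records cannot be linked by patient and knee, say so and report the suture counts as descriptive only.

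The cost is wording changes and a modest re-analysis of existing data, with no new patients or measurements. It depends on records linked by patient and knee, which the text does not confirm.

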### **Ethical approval:**

Approval for the Indus Hospital and Health Network institutional review board was obtained beforehand. (IRB# 2021\_10\_004 )

### **Patient selection:**

All patients aged 50-80 years, belonging to either sex, diagnosed with end-stage osteoarthritis or post-traumatic arthritis, and scheduled for bilateral primary total knee arthroplasty at the Department of Orthopedics, Indus Hospital and Health Network, Karachi were enrolled in the study. Exclusion criteria included patients having existing skin, neuromuscular, or connective tissue disorders, rheumatoid arthritis, immunosuppression, morbid obesity, and pregnancy. All patients provided voluntary informed written consent before enrolment in the study.

### **Intervention:**

In all patients undergoing primary TKA, one knee was closed using polypropylene, whereas the other was closed with Polyglactin 910 sutures. All surgeries were performed by the same surgical team using a standard medial parapatellar approach. The number of sutures and wound closure techniques were standardized across both groups.

### **Outcomes:**

Wound healing was then assessed in the postoperative period at regular intervals (days +3, +7, +15, and +30). Wound-related complications such as surgical site infection (SSI), dehiscence, delayed healing, and Hollander score were recorded. Patient-related outcomes such as pain levels and satisfaction with wound healing were also assessed.

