### **Results:**

A total of forty patients were enrolled in this study. There was a female predominance in the present study, with a M:F ratio of 1:2.07 (Table 1). The median (IQR) age of the study participants was 58 years (50.5 - 69.0 years). Hypertension was the most frequent comorbidity [33(82.5 %)], followed by diabetes mellitus [15 (37.5%)].

At baseline, ASA of Anesthesiologists grade II was the most frequently observed class in the study cohort (85%). The complications and the Hollander score of the patients as observed in the two suture groups are displayed in Table 2. Presentation of erythema was observed in more patients in the polypropylene group versus polyglactin 910 group for postoperative days 3, and 7 i.e. 21 versus 16, and 14 versus 12 respectively but then became vice versa for days 15, and 30 during which the polyglactin 910 group had more patients i.e. 5 versus 3 and 2 versus 0 respectively. The polyglactin 910 group had a higher number of patients in comparison to the polypropylene group for parameters such as wound dehiscence (3 versus 0), wound discharge (24 versus 16), blisters (3 versus 2), stitch abscess (3 versus 1),  $>1$  cm of cellulitis (16 versus 12), step-off border (17 versus 15),  $>2$ mm width scar (10 versus 9), and suture removal due to infection (3 versus 1). The polyglactin 910 group also had a higher of patients with systemic symptoms compared to the polypropylene group (7 versus 4). Poor overall cosmesis was observed in an equal number of patients in both suture groups i.e. 8 (20%). The median Hollander score in both suture groups was reported to be 6. In terms of the correlation coefficient, age [-0.076 (0.042)], weight [-0.121 (0.047)], and presence of diabetes mellitus [-

1.335 (0.741)] had a positive while height [0.095 (0.045)] had a negative correlation on the prediction of Hollander score

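### No outcome or visit is named primary and P<0.05 is tied to no suture comparison, so the suture contrasts in the Results support exploratory statements only and should be reported as paired differences

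*Combined protocol and SAP*

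**What the plan says.** The opening paragraph of Materials and Methods states a general aim: to compare outcomes between two suture materials. The Outcomes section gives two open-ended lists, "Wound-related complications such as surgical site infection (SSI), dehiscence, delayed healing, and Hollander score were recorded" and "Patient-related outcomes such as pain levels and satisfaction with wound healing were also assessed", with this timing: "Wound healing was then assessed in the postoperative period at regular intervals (days +3, +7, +15, and +30". No outcome and no visit is singled out.

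The Statistical analysis section plans description for binary outcomes: "Discrete variables are shown as frequencies and percentages". It names one inferential analysis: "The Hollander score prediction model was used to evaluate the correlation between the Hollander score and all independent variables". It then says "Statistical significance was set at" P < 0.05, without stating which comparisons this covers, whether tests are two-sided, or how multiple tests are handled. It names no test of one suture against the other.

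Under Intervention the comparison is within patients: "one knee was closed using polypropylene, whereas the other was closed with Polyglactin 910 sutures". The opening paragraph calls the trial parallel, and the Randomization section has patients assigned to one of two groups.

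The Results text gives each suture comparison as a pair of counts or medians, with no P-value, effect estimate or interval. Its model coefficients are for age, weight, diabetes and height; none is given for suture.

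**The concern.** The trial asks which closure gives the better outcome, but nothing in the plan says which outcome, at which visit, answers that. The choice matters even within one sign. Erythema is more frequent with polypropylene on days 3 and 7, "but then became vice versa for days 15, and 30 during which the polyglactin 910 group had more patients i.e. 5 versus 3". By day 30 the counts are 2 with polyglactin and none with polypropylene. Naming an outcome without a visit would therefore still leave the answer open.

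Two things are at stake. First, if several contrasts were tested at an unadjusted 0.05, a single small P-value could be presented as the trial's answer although the plan gave that outcome no special place. Second, marginal counts alone do not answer a within-patient question: the same two totals can come from very different pairings, so the reader cannot judge precision.

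**Working it through.** The documents give no sample-size, power or error-rate figure, so there is none to reproduce.

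**Contrasts in the Results text.** Erythema at four visits (4); dehiscence, discharge, blisters, stitch abscess, cellulitis, step-off border, scar width, suture removal for infection, and poor cosmesis (9). 4 + 9 = 13 knee-level binary contrasts. Adding the Hollander score gives 14. Adding systemic symptoms (7 v 4), which are not clearly attributable to one knee, gives 15.

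**Number of pairs.** Forty patients were enrolled, and poor cosmesis is 8 (20%) in each group: 8/0.20 = 40 knees per suture. I assume 40 complete pairs.

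**Smallest possible P.** Two-sided exact McNemar uses only the discordant pairs. For margins a and b, P is smallest when every patient with the event on the less affected side also had it on the other. The discordant split is then |a - b| to 0, and P = 2 x 0.5^|a-b| (at most 1).

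| Contrast | Polypropylene | Polyglactin | Smallest P |
|---|---|---|---|
| Erythema day 3 | 21 | 16 | 0.0625 |
| Erythema day 7 | 14 | 12 | 0.50 |
| Erythema day 15 | 3 | 5 | 0.50 |
| Erythema day 30 | 0 | 2 | 0.50 |
| Dehiscence | 0 | 3 | 0.25 |
| Discharge | 16 | 24 | 0.0078 |
| Blisters | 2 | 3 | 1.00 |
| Stitch abscess | 1 | 3 | 0.50 |
| Cellulitis | 12 | 16 | 0.125 |
| Step-off border | 15 | 17 | 0.50 |
| Scar width | 9 | 10 | 1.00 |
| Suture removal | 1 | 3 | 0.50 |
| Poor cosmesis | 8 | 8 | 1.00 |

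Direction: 10 rows have more events with polyglactin, 2 have more with polypropylene, 1 is equal. Only discharge can fall below 0.05. With no shared patients its split is 24 to 16 and P = 0.268. It crosses 0.05 between 13 shared (11 to 3, P = 0.057) and 14 shared (10 to 2, P = 0.039). Erythema day 3 ranges from 0.0625 to 0.51.

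**Paired difference, polyglactin minus polypropylene.** Adjusted Wald: add 0.5 to each of the four paired cells, so N = 42. With b* and c* the adjusted polyglactin-only and polypropylene-only counts, d = (b* - c*)/42 and SE = sqrt[(b* + c*) - (b* - c*)²/42]/42.

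- Discharge, raw difference 8/40 = 20 points. With 16 shared: d = 0.190, SE = sqrt(9 - 1.524)/42 = 0.065, 95% CI 6 to 32 points. With none shared: SE = sqrt(41 - 1.524)/42 = 0.150, 95% CI -10 to 48.
- Erythema day 3, raw difference -5/40 = -12.5 points. With 16 shared: d = -0.119, SE = sqrt(6 - 0.595)/42 = 0.055, 95% CI -23 to -1. With none shared: SE = sqrt(38 - 0.595)/42 = 0.146, 95% CI -40 to 17.

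At the first of these erythema pairings the approximate interval just excludes zero while the exact P is 0.0625. The two methods disagree at the margin, so that interval should not be read as significance.

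**Chance of any false positive if contrasts were tested at 0.05.** Null simulation, 4,000 runs per setting, pooled rates from the Results, 40 pairs, latent-normal correlations of 0, 0.3 and 0.6 between knees and between outcomes, exact McNemar. All 13 binary contrasts: about 15-21%. Five of them only (erythema days 3 and 7, discharge, cellulitis, step-off): about 10-14%. The rate therefore passes 5% well before every contrast is tested.

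**The case against.** The strongest reply is that no error has been committed. Binary outcomes were planned as frequencies and percentages, the threshold directly follows the model sentence and most naturally governs that model, and the Results text makes no suture significance or superiority claim. This stands: the multiplicity risk is conditional. A reader might infer that the sponsor picked a convenient result. The documents do not support that.

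It can also be said that the Hollander score, as the only modelled outcome, is an implicit primary. It is a focus, but it is never called primary and has no visit, and the text reports no suture coefficient. Both medians (6 and 6) are already known, so naming it now would be post hoc.

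A reader might quote 1 - 0.95^14 = 51% or 1 - 0.95^15 = 54% as the error rate. Those figures need independent tests of full 5% size. Exact McNemar on counts this small is conservative, and outcomes on the same knees are likely to be correlated, so they do not apply.

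A reader might also say that the contrasts scatter in both directions. They do not scatter evenly: both reversals are erythema at the two early visits. Nor are the ten contrasts with more polyglactin events ten separate confirmations, since several plausibly overlap (discharge, cellulitis, stitch abscess, suture removal for infection).

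Finally, Table 2 is not shown and one passage was removed before review. Statements about what is not reported are limited to the visible text.

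**Conclusion.** The concern holds in a limited form. The plan as written names no primary outcome or visit, no suture-versus-suture analysis and no scope for its threshold, so the suture contrasts support exploratory statements only. Testing all 13 binary contrasts at an unadjusted 0.05 would carry about a 15-21% chance of at least one false positive. On the reported margins just one of them, discharge, could be nominally significant, and only if at least 14 of the 16 patients with polypropylene-side discharge also had it on the other side.

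Equal Hollander medians might be read as showing no difference between sutures; they do not exclude a within-patient difference.

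These figures assume 40 complete pairs with one knee per suture, as Intervention describes. The simulation also rests on the assumed correlations. The parallel, patient-level wording elsewhere conflicts with that design and would have to be resolved before any paired analysis. This is a point the sponsor should act on, with medium confidence, because the remedy is labelling and better reporting rather than correction of a visible false claim.

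**What to change.** In Outcomes and Statistical analysis:

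1. Unless a dated document shows a primary outcome and visit fixed before the data were seen, label all suture comparisons exploratory and make no significance or superiority claim.
2. If such a document exists, test that one outcome at that visit with a paired test at two-sided 0.05 and treat the rest as secondary.
3. Disclose any primary named now, including the Hollander score, as post hoc.
4. State which analyses P<0.05 governs, and whether suture type was among the model's independent variables.
5. Reconcile the one-knee-per-suture description in Intervention with the parallel label in the opening paragraph and the patient-level assignment in Randomization. Then report each knee-level outcome as its four paired counts (both knees, polypropylene only, polyglactin only, neither) and the within-patient difference with a 95% CI, in place of marginal frequencies alone.

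The cost is wording plus a recount of paired cells from data already collected. The downside is that, without a dated pre-specification, the trial makes no confirmatory claim.
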